4.2. Exclusion Criteria

Participants meeting any of the following exclusion criteria will not be eligible for study enrollment:

- 1. RBC transfusion within 3 months before initiation of study drug
- 2. Planned initiation of regularly scheduled RBC transfusion therapy (also termed chronic, prophylactic, or preventive transfusion) during the study
- 3. Hospitalization for VOC or acute chest syndrome (ACS) within 30 days prior to informed consent/assent.
- 4. More than 10 VOCs requiring hospitalization, emergency department or clinic visit within the past 12 months
- 5. Planned elective surgery within the next 6 months
- 6. Physical inactivity attributable to clinically significant musculoskeletal, cardiovascular, or respiratory comorbidities
- 7. Anemia due to bone marrow failure (eg, myelodysplasia)
- 8. Absolute reticulocyte count (ARC) $< 100 \times 10^{9}/L$
- 9. Screening alanine aminotransferase $(ALT) > 4 \times upper limit of normal (ULN)$
- 10. Severe renal dysfunction (estimated glomerular filtration rate < 30 mL/min/1.73 m² by Schwartz formula) or is on chronic dialysis
- 11. Known active hepatitis A, B, or C or who are known to be human immunodeficiency virus (HIV) positive.
- 12. Females who are breast-feeding or pregnant
- 13. Major surgery within 8 weeks before enrollment. Participants must have completely recovered from any previous surgery before enrollment
- 14. History of hematopoietic stem cell transplant or gene therapy
- 15. Received an investigational drug within 30 days or 5-half-lives, whichever is longer, prior to consent, or is currently participating in another trial of an investigational or marketed drug (or medical device)
- 16. Use of concomitant medications (eg, crizanlizumab) that confound the ability to interpret data from the study
- 17. Medical, psychological, or behavioral condition that, in the opinion of the investigator, would confound or interfere with evaluation of safety and/or efficacy of the study drug, prevent compliance with the study protocol, preclude informed consent, or render the participant unable/unlikely to comply with the study procedures
- 18. Use of herbal medications (eg, St. John's Wort), sensitive cytochrome P450 (CYP) 3A4 substrates with a narrow therapeutic index, strong CYP3A4 inhibitors, or fluconazole
- 19. Symptomatic COVID-19 infection

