	8. Absolute reticulocyte count (ARC) $< 100 \times 10^9/L$
	9. Screening alanine aminotransferase (ALT) > $4 \times$ upper limit of normal (ULN)
	10. Severe renal dysfunction (estimated glomerular filtration rate < 30 mL/min/1.73 m ² by Schwartz formula) or is on chronic dialysis

	11. Known active hepatitis A, B, or C or known to be human immunodeficiency virus (HIV)-positive.
	12. Females who are breast-feeding or pregnant
	13. Major surgery within 8 weeks before enrollment. Participants must have completely recovered from any previous surgery before enrollment
	14. History of hematopoietic stem cell transplant or gene therapy
	15. Received an investigational drug within 30 days or 5-half-lives, whichever is longer, prior to consent, or is currently participating in another trial of an investigational or marketed drug (or medical device)
	16. Use of concomitant medications (eg, crizanlizumab) that confound the ability to interpret data from the study
	17. Medical, psychological, or behavioral condition that, in the opinion of the investigator, would confound or interfere with evaluation of safety and/or efficacy of the study drug, prevent compliance with the study protocol; preclude informed consent; or, render the participant unable/unlikely to comply with the study procedures
	18. Use of herbal medications (eg, St. John's Wort), sensitive cytochrome P450 (CYP) 3A4 substrates with a narrow therapeutic index, strong CYP3A4 inhibitors, fluconazole, or moderate or strong CYP3A4 inducers
	19. Symptomatic coronavirus disease of 2019 (COVID-19) infection
Concomitant	The following concomitant medications are allowed :
Medications and Restrictions	• HU (stable dose for at least 3 months before signing the ICF and with no dose modifications planned or anticipated and no sign of hematological toxicity)
	• Glutamine
	• ESAs (stable dose for at least 4 weeks with no dose modifications planned or anticipated by the investigator)
	The following concomitant medications are prohibited :
	• Sensitive CYP3A4 substrates with a narrow therapeutic range
	Strong CYP3A4 inhibitors or fluconazole
	Moderate and strong CYP3A4 inducers
	Crizanlizumab (Adakveo [®])
	Other experimental SCD therapy
Study Endpoints	All endpoints in this study are exploratory and include:
	• Change in total daily physical activity (expressed in counts per minute) from baseline to Week 10-12 and to Week 22-24

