4.1. Inclusion Criteria

Participants who meet all of the following inclusion criteria will be eligible for study enrollment:

- 1. Male or female with SCA (HbSS or [HbS β^0]thal genotype)
- 2. Age 12 to 55 years, inclusive
- 3. Hb \leq 8.0 g/dL during screening
- 4. Treatment with HU therapy on study is permitted if the participant has been on a stable dose for at least 90 days before enrollment with no dose modifications planned or anticipated by the investigator
- 5. Treatment with glutamine is permitted
- 6. Treatment with erythropoiesis-stimulating agents (ESAs) is permitted if the participant has been on a stable dose for at least 12 weeks before enrollment with no dose modifications planned or anticipated by the investigator
- 7. Female participants of child-bearing potential must use highly effective methods of contraception to 30 days after the last dose of study drug. Male participants must use barrier methods of contraception to 30 days after the last dose of study drug.
- 8. Females of child-bearing potential and postmenopausal females are required to have a negative pregnancy test before the administration of study drug
- 9. Written informed consent and participant assent per IRB policy and requirements, consistent with International Council and Harmonisation (ICH) guidelines

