6.3. Demographics and Medical History

Demographic and baseline characteristics of sex, race, ethnicity, age, weight, and height of the participant will be collected at time of screening.

Clinically significant medical history (as determined by the investigator) will be recorded at the time of the screening.

Medical history includes clinically significant disease manifestations, comorbid conditions, surgeries, and all medications used by participant within 30 days prior to screening.

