6.8. Patient-Reported Outcomes

Patient-reported outcomes will be evaluated using the National Institute of Health Patient Reported Outcome Measurement Information System (PROMIS) short forms and the PGIC survey provided by the Sponsor. The following assessments will be used to collect QOL measures:

- PROMIS Pediatric Profile-37 v2.0 (for pediatric participants)
- PROMIS-43 V2.1 (for adult participants)
- PGIC

PRO assessments will be self-administered by study participants at scheduled study visits, as specified in the SOA.

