8.2. Sample Size

Approximately 50 participants who are 12 through 55 years of age (inclusive) with SCD and chronic moderate anemia will be enrolled and treated with voxelotor in this study.

8.3. **Populations for Analysis**

All participants who receive at least 1 dose of study treatment will be included in the safety population. This is the analysis population used to summarize all efficacy and safety data.

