- ^f Hematology assessments will include %HbF (screening only), WBC (with differential), RBC count, Hb, hematocrit, RDW, MCH, MCHC, MCV, platelet count, reticulocyte percentage, and absolute reticulocyte count. Serum chemistry will include sodium, potassium, bicarbonate, chloride, calcium, phosphorus, BUN, creatinine, glucose, bilirubin (total, direct, and indirect), total protein, albumin, ALT, alkaline phosphatase, AST, LDH, and serum erythropoietin.

^g PRO assessments to be completed during Run-in Period prior to start of treatment on Day 1.

^h Nocturnal SpO₂ device will be dispensed at Week -2 (Run-in Period) and at Weeks 2, 12, and 24. Measurements will be performed for 2 consecutive nights and the device should be returned within 48 hours after the measurements have been performed.

Figure 1: Study Schematic

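### Exclusion 10 prescribes the pediatric Schwartz formula, with no constant stated, as the only eGFR equation for ages 12 to 55, so the threshold of 30 is not applied uniformly in adults

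*Protocol*

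**What the plan says.** Section 4.2, exclusion 10, reads "Severe renal dysfunction (estimated glomerular filtration rate < 30 mL/min/1.73 m² by Schwartz formula) or is on chronic dialysis". The synopsis carries the same criterion and also ends "by Schwartz formula) or is on chronic dialysis". Inclusion 2 in Section 4.1 sets the population as "Age 12 to 55 years, inclusive", and Section 8.2 plans about 50 participants over that range with no adolescent/adult split.

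The protocol does not restrict Schwartz to adolescents, name a second equation for adults, or say which Schwartz version or constant applies. It does separate instruments by age elsewhere: Section 6.8 assigns one PROMIS profile to pediatric and another to adult participants.

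The inputs for any creatinine equation are available. Section 6.3 states "Demographic and baseline characteristics of sex, race, ethnicity, age, weight, and height of the participant will be collected at time of screening", and serum creatinine is in the screening chemistry panel (Table 5 and Appendix 1).

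**The concern.** The Schwartz formula is a constant times height divided by serum creatinine. It is an equation for children and adolescents. With no age term, it gives a 15-year-old and a 55-year-old of equal height and creatinine the same value. Its single-constant form also has no sex term. The protocol does not say that Schwartz is pediatric; this is general knowledge of the method it names. Exclusion 10 nonetheless prescribes the formula for every adult in the study.

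An eligibility rule has to be applied as written. A site that follows this one literally uses a pediatric equation for a 50-year-old. A site that uses an adult eGFR departs from the criterion. Because the constant is not given, two sites that both comply can still reach different answers. Section 1.1.1 names anemia as a risk factor for renal complications in sickle cell disease, so impaired renal function is foreseeable in this population.

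This is not a detail left to the SAP. Eligibility belongs in the protocol, and the text does specify an equation, for everyone.

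**Working it through.** The protocol reports no eGFR result to reproduce; the only stated figure is the threshold of 30 mL/min/1.73 m². The check asks what adult-equation eGFR a Schwartz value of exactly 30 corresponds to.

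**Inputs from the protocol:** threshold 30; Schwartz formula; ages 12 to 55.

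**Assumptions outside the protocol:** k = 0.413 or 0.55 (0.7 as an extreme), since no constant is stated; height 163 cm for women and 178 cm for men; CKD-EPI 2021 as the adult comparator.

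**Step 1. Creatinine at which Schwartz equals 30:** Scr = k × height / 30.
- Woman, k = 0.413: 0.413 × 163 / 30 = 2.24 mg/dL
- Woman, k = 0.55: 0.55 × 163 / 30 = 2.99 mg/dL
- Man, k = 0.413: 0.413 × 178 / 30 = 2.45 mg/dL
- Man, k = 0.55: 0.55 × 178 / 30 = 3.26 mg/dL

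**Step 2. Adult equation at that creatinine.** At these values it is 142 × (Scr/κ)^−1.2 × 0.9938^age, times 1.012 for women, with κ = 0.7 (women) or 0.9 (men).
- Woman aged 50, k = 0.413: 142 × 0.2471 × 0.7327 × 1.012 = 26.0
- Woman aged 50, k = 0.55: 142 × 0.1753 × 0.7327 × 1.012 = 18.5
- Man aged 30, k = 0.413: 142 × 0.3007 × 0.8298 = 35.4

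Adult-equation eGFR when Schwartz reads 30:

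| | Age 18 | Age 30 | Age 50 | Age 55 |
|---|---|---|---|---|
| Woman, k = 0.413 | 31.8 | 29.5 | 26.0 | 25.2 |
| Man, k = 0.413 | 38.2 | 35.4 | 31.3 | 30.3 |
| Woman, k = 0.55 | 22.5 | 20.9 | 18.5 | 17.9 |
| Man, k = 0.55 | 27.1 | 25.1 | 22.2 | 21.5 |

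For ages 30 to 55 the range is about 25 to 35 with k = 0.413 and about 18 to 25 with k = 0.55. Including age 18 raises the upper ends to about 38 and 27.

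**Step 3. Width of the discordant band (k = 0.413).** The adult equation reaches 30 at these creatinine values:
- Woman aged 50: 1.99 mg/dL. Between 1.99 and 2.24 she is admitted by Schwartz although the adult equation puts her below 30.
- Man aged 30: 2.81 mg/dL. Between 2.45 and 2.81 he is excluded by Schwartz although the adult equation puts him above 30.
- Man aged 50: 2.54 mg/dL, against a Schwartz cut-off of 2.45. The two rules nearly coincide.

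**Step 4. Same patient, two constants.** For a woman of 163 cm with creatinine 2.5 mg/dL, 0.413 × 163 / 2.5 = 26.9 (excluded) and 0.55 × 163 / 2.5 = 35.9 (admitted). Both results comply with the text.

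**Sensitivity.** With heights of 150 to 175 cm (women) and 160 to 190 cm (men), ages 18 to 55 and k up to 0.7, a Schwartz value of 30 maps to an adult-equation eGFR of roughly 12 to 43. With k = 0.413 the discrepancy goes both ways. With 0.55 or 0.7 Schwartz is almost always the more permissive rule.

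**The case against.** The case against is mainly about weight, and much of it stands.

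- **The threshold is not at fault.** A reader might infer that the cut-off of 30 is itself invalid. Nothing in the protocol supports that; the problem is the equation used to reach 30.
- **Discordant is not the same as wrong.** A reader might also infer that every decision near the threshold is mistaken. The figures do not show this. Decisions differ only inside a limited creatinine band, and for a 50-year-old man with k = 0.413 the two equations nearly agree. The comparator is another estimate from the same creatinine, not measured GFR.
- **The larger gaps depend on the constant.** Values around 18 need k = 0.55, and the low end of the wide range needs k = 0.7. No evidence shows that a site would use either in an adult. Disagreement between sites is possible under the text but not documented.
- **There are partial backstops.** Chronic dialysis is excluded without any formula. Exclusion 17 lets the investigator exclude a condition that would interfere with safety evaluation. Serum chemistry is repeated on Day 1 and at Weeks 2, 12 and 24. These soften the effect of admitting a borderline adult but do nothing for an adult excluded by the equation.
- **The consequence is limited.** No endpoint in Section 8.1 uses renal function, and the study is single-arm, exploratory and descriptive. Section 1.1.1 is background and does not tie renal function to the safety of the study drug.

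What remains is that both statements of the criterion prescribe one pediatric equation for a largely adult age range and leave its constant open. The backstops do not correct that.

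**Conclusion.** The point holds as a fault in the eligibility specification. Exclusion 10 makes Schwartz the only eGFR equation for ages 12 to 55 without stating its constant, so the threshold of 30 is not applied uniformly in adults.

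The text of the criterion settles that much, together with the general knowledge that Schwartz is a height-based pediatric equation. The size is illustrative and rests on the assumed heights, constants and comparator shown above. The protocol gives no eGFR distribution, so the number affected cannot be calculated. It is likely to be few of about 50 and may be none. No endpoint or sample-size figure changes. It should be corrected because the criterion cannot be applied consistently as written, not because it threatens the study's results.

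**What to change.** In exclusion 10, in both Section 4.2 and the synopsis, keep the threshold of 30 mL/min/1.73 m² and the dialysis clause, and specify the equation by age group:

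- under 18 years: Schwartz, with its version or constant stated;
- 18 years and older: a named creatinine-based equation validated in adults.

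The cost is one line in each of two places. Creatinine, height, age and sex are already collected at screening, so no test or visit is added.

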5. TREATMENTS ADMINISTERED

5.1. Treatment Regimen

Participants will be instructed to take 1500 mg of voxelotor (three 500 mg tablets) orally once daily for 24 weeks (168 days).

Instructions for administration of voxelotor tablets:

- Details regarding oral administration of the voxelotor tablets are provided in the Pharmacy Manual (provided separately).
- For younger participants, voxelotor administration should be supervised by a parent or guardian. Detailed instructions will be provided to participants and their caregivers/legal guardians prior to the first dose of study drug.

Treatment compliance will be based on comparison of the dispensed versus returned study drug.

At assigned visits, participants will be supplied a sufficient quantity of voxelotor to ensure continuous dosing through to the next dispensing visit. All study drug packaging must be returned at designated visits, regardless of whether it is empty or contains unused study drug.

5.2. Dose Frequency

Participants will receive a 1500 mg dose of voxelotor as three 500 mg tablets administered orally, once daily. If a participant misses a dose, the participant should resume normal dosing the next day (ie, the dose on the day after a day of a missed dose should not be increased or decreased).

5.3. Dose Modification

Participants should adhere to their assigned dose level. However, dose modification may be considered if warranted as outlined in Table 1.

All instances of study drug modification (dose reduction, interruption, or discontinuation) should be documented in the participants' medical record and recorded in the electronic case report form (eCRF). If the condition/event leading to the dose modification has resolved, the original dose level should be resumed, unless in the judgment of the investigator this cannot be done safely.

Dose Reduction				
Event	Recommended Action			
Grade \geq 2 (NCI grading scale) AE deemed considered related to study drug by the Investigator AND Precludes continued dosing at the current dose level due to safety concern or lack of tolerability (in the Investigator's judgment)	Study drug: May be reduced by one (1) tablet. If, in the opinion of the Investigator, a Grade 2 AE has resolved to ≤ Grade 1, participant may resume study drug at the original dose. If, in the opinion of the Investigator, the AE poses a significant safety concern such that a dose hold is considered, the Investigator should contact the Medical Monitor.			
Dose Interruption (Hold)				
Event	Recommended Action			
$\frac{\text{Grade} \geq 3 \text{ (NCI grading scale) AE}}{\text{considered related to study drug by the Investigator}}$ AND Precludes continued dosing at the current or at a reduced dose level due to safety concern or lack of tolerability in the Investigator's judgment	Study drug: Hold dose until \leq Grade 2, then resume study drug at original dose. If, in the opinion of the Investigator, dosing should be resumed at a lower dose, contact the Medical Monitor for further discussion. If the AE recurs or worsens, reduce dose by one tablet. Maximum dose hold is 5 continuous days. If, in the opinion of the Investigator, a longer dose hold is clinically needed, the Medical Monitor should be contacted for discussion.			
Drug Discontinuation				
Event	Recommended Action			
Grade \geq 3 study drug-related AE that, at the discretion of the Investigator, warrants discontinuation of study drug (eg, has not improved or resolved after dose hold).	Study drug: Discontinue study drug. If the Investigator considers that the participant would benefit from continuing treatment, the Medical Monitor should be contacted.			

Dose Modification Guidelines for Study Drug-Related Adverse Events Table 1:

Abbreviations: AE, adverse event; SAE, serious adverse event.

5.4. **Physical Description**

Voxelotor is a synthetic small molecule bearing the chemical name 2-hydroxy-6-((2-(1-isopropyl-1H-pyrazol-5-yl) pyridin-3-yl) methoxy) benzaldehyde. The chemical formula is $C_{19}H_{19}N_3O_3$ and the molecular weight is 337.4 g/mol.

5.5. Formulation

Voxelotor (500 mg) tablets contain voxelotor drug substance along with several formulation excipients. All excipients used for the formulation are listed in the US FDA Inactive Ingredient Database (IID) or are pharmaceutical excipient mixtures entirely composed of FDA IID listed components.

5.6. **Packaging and Labeling**

Voxelotor tablets will be supplied to clinical sites in high-density polyethylene bottles with induction-sealed polypropylene child-resistant caps. Additional details are provided in the Pharmacy Manual.

5.7. Study Drug Supply

The Sponsor or its representative will supply the packaged and labeled drug product to the clinical sites. Study drug will be dispensed at the Day 1 visit and at the Week 12 visit. Participants will receive a 3-month (90-day) supply of study drug at each dispensation visit. Additional details are provided in the Pharmacy Manual.

5.8. Storage and Handling Procedure

All study drug will be stored at controlled room temperature between 15°C to 25°C (59°F to 77°F) in the storage area of the investigational site pharmacy, which must be a secure, temperature-controlled, locked environment with restricted access.

No special procedures are required for the safe handling of the study drug. The Sponsor (or its representatives) will be permitted (upon request) to audit the supplies, storage, dispensing procedures, and records.

5.9. Drug Accountability and Retention

In accordance with Good Clinical Practice (GCP), the investigational site will account for all supplies of the study drug. Details of receipt, storage, assembly, and return will be recorded. The lot numbers for the study drug will be provided to the site by the supplier/manufacturer as soon as they are available.

The investigator (or designee) will maintain an accurate record of the receipt of the study drug as shipped by the Sponsor (or designee), including the date received and storage conditions/location. In addition, an accurate drug disposition record will be kept, specifying amount dispensed to each participant, the date of dispensation, the date of return, the number of tablets returned, and destruction records. A copy of this record will be returned to the Sponsor when the contents and condition of the study drug shipment have been verified.

Current dispensing records will also be maintained, including the date and amount of study drug dispensed and the participant receiving the drug. This drug accountability record will be available for inspection at any time.

All unused supplies of voxelotor will either be destroyed by the investigational site or returned to the Sponsor's designated location throughout and at the end of the study in accordance with instruction by the Sponsor.

Additional details are provided in the Pharmacy Manual (provided separately).

5.10. Treatment of Overdose

Based on the mechanism of action of voxelotor, an extreme overdose might decrease oxygen delivery to tissues. Transfusion, exchange transfusion, and/or hyperbaric oxygen therapy may be administered in the event of a medical emergency due to a suspected voxelotor overdose.

Guidelines for reporting a suspected treatment overdose are provided in Section 7.5.

5.11. Concomitant Medications

A concomitant medication is defined as any prescription or over-the-counter preparation, including vitamins and supplements.

In the interests of participant safety and acceptable standards of medical care, the investigator will be permitted to prescribe treatment(s) at his/her discretion. For all participants who initiate treatment, all administered concomitant medications from signing the informed consent until 28 days after the participant's last dose of study drug, must be recorded in the participants' eCRF (medication, dose, treatment duration, and indication).

Penicillin prophylaxis and vaccinations (including the COVID-19 vaccine) are allowed in accordance with standard of care.

All reported prior and concomitant medications will be coded using the current version of the World Health Organization Drug Dictionary.

